12.2.1 Complete Remission (CR)

Attainment of an M1 bone marrow (< 5% blasts) with no evidence of circulating blasts or extramedullary disease and with recovery of peripheral blood counts (ANC $\geq 1000/\text{mm}^3$ and platelet count $\geq 100,000/\text{mm}^3$). Occasionally, rare peripheral blood blasts may be identified during marrow regeneration; however, the marrow must be M1 status by morphology and without Auer rods to be considered CR. Flow cytometry may also be useful to distinguish between leukemia and a regenerating bone marrow. There is no requirement for bone marrow cellularity.

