12.2.2 CR with Partial Recovery of Platelet Count (CRp)

Attainment of an M1 bone marrow (< 5% blasts), no evidence of circulating blasts or extramedullary disease, and recovery of ANC $\geq 1000/\text{mm}^3$ and platelet transfusion independence (defined as no platelet transfusions in 1 week).

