12.2.3 CR with incomplete blood count recovery (CRI)

Attainment of an M1 bone marrow (< 5% blasts), no evidence of circulating blasts or extramedullary disease and with ANC $< 1000/\text{mm}^3$ or platelet count $< 100,000/\text{mm}^3$ without platelet transfusion independence (defined as no platelet transfusions in 1 week).

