12.2.4 Partial Response (PR)

A decrease of at least 50% in the percentage of blasts to 5% to 25% in the bone marrow aspirate. Bone marrow must have adequate cellularity (e.g., > 15%) to determine response. PR status will not be included in calculation of response to the regimen. A repeat bone marrow aspiration after several weeks may be required to distinguish between a PR and increased blasts caused by bone marrow regeneration. A value of < 5% blasts may also be considered a PR if Auer rods are present.

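### The Auer-rod exclusion and the regenerating-blast allowance are written into CR but not into CRp or CRi, so some M1 marrows can be read as remission or PR and others fall to stable disease

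*Combined protocol and SAP*

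**What the plan says.** All three remission categories require an M1 marrow. Only CR (12.2.1) qualifies that requirement:

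- Auer rods: "the marrow must be M1 status by morphology and without Auer rods to be considered CR".
- Circulating blasts: "Occasionally, rare peripheral blood blasts may be identified during marrow regeneration".

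CRp (12.2.2) reads "Attainment of an M1 bone marrow (< 5% blasts), no evidence of circulating blasts or extramedullary disease, and recovery of ANC" to the stated level, plus a week free of platelet transfusion. CRi (12.2.3) reads "Attainment of an M1 bone marrow (< 5% blasts), no evidence of circulating blasts or extramedullary disease and with ANC" below that level, or low platelets without transfusion independence. Neither mentions Auer rods or regeneration.

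PR (12.2.4) is ordinarily "A decrease of at least 50% in the percentage of blasts to 5% to 25% in the bone marrow aspirate". It then adds "A value of < 5% blasts may also be considered a PR if Auer rods are present", and states that "PR status will not be included in calculation of response to the regimen". SD (12.2.6) is the residual category. Best response is taken over up to four cycles (12.2). The PK and immunogenicity comparisons divide patients by CR/CRi status (8.2.1, 8.3.1).

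**The concern.** Response categories should not overlap where the choice changes a patient's responder status, and they should leave no remission marrow without a home. Here the text falls short in two ways.

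First, a marrow with Auer rods can be filed as CRi or CRp, or as PR. PR is outside the response calculation, whereas CRi is on the responder side of the PK and anti-drug-antibody comparisons. In an open-label trial that choice would be made with dose and clinical course known.

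Second, the allowance for regenerating blasts is attached only to the category with full counts, although counts are typically still incomplete during regeneration. A child who differs from a CR only in counts then has no remission category.

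At stake are the descriptive activity estimate (aim 1.2.2) and, for CRi, the CR/CRi split. The SD or PD reading also touches the rule that ends protocol therapy when PR is not reached after Cycle 2 (5.2, 10.1).

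**Working it through.** The plan states no response rate, so there is no figure of its own to reproduce. The check sets the definitions side by side and then enumerates the cases.

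| Category | Auer rods | Circulating blasts | Counts |
|---|---|---|---|
| CR, 12.2.1 | must be absent | none, but rare regenerating blasts tolerated | ANC ≥1000 and platelets ≥100,000 |
| CRp, 12.2.2 | not mentioned | none, no allowance | ANC ≥1000, transfusion independent; no upper platelet limit |
| CRi, 12.2.3 | not mentioned | none, no allowance | ANC <1000, or platelets <100,000 without transfusion independence |
| PR at <5% blasts, 12.2.4 | present | not mentioned | not mentioned |
| PD, 12.2.5 | not mentioned | rise of at least 50% from nadir, no regeneration exception | not mentioned |

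**Assumptions.** Marrow below 5% blasts, adequate cellularity, no extramedullary disease, PD not met. Platelets ≥100,000 imply transfusion independence. In CRi, the transfusion condition is read as attached to the platelet limb only. The PR option is counted as available whenever Auer rods are present.

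**Profiles.** Auer rods (2) × rare circulating blasts (2) × ANC at or below the limit (2) × platelet state (3: ≥100,000; lower but transfusion independent; lower and dependent) = 24.

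**Literal result, six profiles in each block:**

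- Auer rods, no circulating blasts: 4 are CRi and PR; 2 are CRp and PR. One of the latter has full counts: it is barred from CR by Auer rods yet still meets CRp.
- No Auer rods, rare circulating blasts: 1 is CR (full counts); the other 5 meet none of CR, CRp, CRi or PR and default to SD.
- No Auer rods, no circulating blasts: 4 are CRi; 1 is CRp; 1 (full counts) is both CR and CRp.
- Auer rods and circulating blasts: all 6 can only be PR among the response categories.

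So 6 of 24 profiles straddle PR and a remission category, 5 of 24 fall to SD, and 1 of 24 is both CR and CRp.

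**Effect of aligning the wording.** Excluding Auer rods from CRp and CRi takes the 6 to 0. If the regeneration allowance also applied to CRp and CRi, the 5 would go to 0, but profiles that are both CR and CRp would rise from 1 to 2, because CRp has no platelet ceiling. A stated order settles those two. Order alone would not suffice: with CRp and CRi ahead of PR and no Auer-rod exclusion, all 6 Auer-rod profiles would become remissions.

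**Size.** One reclassified child shifts a response proportion by 1/n. Section 11.1 gives a maximum of 18 evaluable patients for the MTD/RP2D and up to 6 more for PK, so n = 18 or 24:

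- 1/18 = 5.6 points
- 1/24 = 4.2 points
- At the enrollment ceilings of 27 and 47: 1/27 = 3.7 and 1/47 = 2.1 points

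The profile counts are logical combinations, not expected frequencies.

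**The case against.** The strongest reply is that the intent is clear. CRp and CRi are titled as forms of CR, so CR's qualifiers carry over. The relapse definition (12.2.7) treats CR, CRp and CRi together and excuses blasts explained by marrow regeneration. The criteria are tied to published AML criteria (11.5, 12.2), and response is descriptive with no hypothesis.

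Much of this stands as evidence of intent. But 12.2.7 governs relapse, not attainment; no carry-over is stated; and each definition repeats CR's other elements in full. Whether the cited criteria supply the missing qualifiers cannot be judged from these documents.

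Four stronger readings are tempting and not supported:

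- *The plan forces a double classification.* It does not. The PR wording is permissive, so the defect is an unresolved choice.
- *A regenerating marrow ends up as SD.* Only if PD is not met (with a circulating-blast nadir of zero, rare blasts could literally be read as PD) and only if no later marrow in the four-cycle window supersedes it.
- *Copying CR's qualifiers gives every marrow exactly one category.* It does not, because CR and CRp still overlap at full counts.
- *The response rate will be materially distorted.* The documents give no frequency for either pattern.

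That CRi counts as a response is itself inferred, from the CR/CRi groupings and from only PR being expressly excluded. The PK and immunogenicity splits do not name CRp, so the CRp overlap has no clear route into them.

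**Conclusion.** The point holds as a wording defect in a descriptive secondary endpoint. On the literal text, an M1 marrow with Auer rods and no circulating blasts can be placed on either side of the responder line, with no rule to decide. An M1 marrow without Auer rods, with rare regenerating blasts and counts short of CR, has no remission category. Each affected child is worth 5.6 points at n=18 or 4.2 points at n=24, assuming all those patients are evaluable for response; the number affected is unknown and may be zero. DLT assessment, the MTD/RP2D and the sample size are untouched.

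The Auer-rod choice does not alter continuation after Cycle 2 if CRp and CRi are taken as at least PR. The SD or PD reading can bear on it. A reader might infer that a child would be wrongly taken off therapy; the documents show only that the passages do not fit together, and this review takes no position on the rule.

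**What to change.** For the response analysis:

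1. In 12.2.2 and 12.2.3, state that the marrow must be M1 without Auer rods, as in 12.2.1.
2. In 12.2.4, state definitely that a marrow below 5% blasts with Auer rods is not counted as CR, CRp or CRi.
3. State that categories are assigned in the order CR, CRp, CRi, PR, which also settles the CR/CRp overlap.
4. Reconcile the circulating-blast wording of 12.2.2, 12.2.3 and 12.2.5 with the regeneration allowance in 12.2.1.
5. Reconcile these sections with the Cycle 2 continuation rule in 5.2 and 10.1. The content of that rule is for the sponsor.

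The cost is a few sentences in Section 12.2 and a cross-check of 5.2 and 10.1. No new data or samples are needed. The reported response count could move by a patient in either direction.

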12.2.5 Progressive Disease (PD)

Increase in the absolute number of circulating (in peripheral blood) or bone marrow blasts of at least 50% from nadir or development of extramedullary disease.

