If a patient experiences progressive disease at any time point, they must discontinue protocol therapy. Patients with at least a partial response (PR) following Cycle 2 may continue on subsequent cycles of flotetuzumab for a total of up to 6 cycles. Patients should discontinue protocol therapy if they have not achieved at least a PR following Cycle 2. No planned step-up dosing will occur during subsequent cycles unless there is an infusion interruption of > 3 days between cycles of flotetuzumab. For patients with no evidence of disease after Cycle 1, subsequent cycles should be interrupted until ANC $\geq 500 \mu\text{L}$ and platelets $\geq 20,000/\text{mm}^3$. Patients with persistent disease are permitted to continue flotetuzumab regardless of ANC and platelet counts.

Pharmacokinetic sampling and monitoring for ADAs will be performed in all patients (see [Appendix VI-A](#), [Appendix VI-B](#), [Appendix VI-C](#), and [Appendix VII](#)). In consenting patients, correlative studies to characterize the tumor microenvironment will be obtained, which will include peripheral blood studies and bone marrow (see [Appendix X](#) and [Appendix XII](#)). Correlative plasma studies as a measurement of CRS and biomarkers of response will also be obtained in consenting patients (see [Appendix XI](#)).

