12.2.7 Relapse

Morphologic relapse after CR/CRp/CRI is defined as a reappearance of leukemic blasts in the peripheral blood or $\geq 5\%$ blasts in the bone marrow not attributable to any other cause (e.g., bone marrow regeneration after consolidation therapy). In the setting of recent treatment, if there are no circulating blasts and the bone marrow contains 5% to 20% blasts, a repeat bone marrow performed at least a week later is necessary to distinguish relapse from bone marrow regeneration. Should flow cytometric analyses suggest relapse (by the reappearance of a similar immunophenotype to the original leukemia) in the presence of < 5% blasts, or $\geq 5\%$ blasts in a regenerating marrow, a repeat bone marrow(s) performed at least a week later is necessary to confirm relapse by morphologic methods. In such instances the date of recurrence is defined as the first date that more than 5% blasts were observed in the marrow. The

THIS PROTOCOL IS FOR RESEARCH PURPOSES ONLY, SEE PAGE 1 FOR USAGE POLICY

reappearance or development of cytologically proven extramedullary disease also indicates relapse. Molecular and/or genetic relapse is characterized by reappearance of a cytogenetics or molecular abnormality.

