12.2.8 Unevaluable

Aplastic or severely hypocellular marrow with any blast percentage. In this instance, marrow evaluation should be repeated weekly until response determination can be made through at least Day 49.

12.2.9 Bone Marrow Classification:

M1 is < 5% blasts
M2 is 5-25% blasts
M3 is > 25% blasts

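### Progressive disease in 12.2.5 has no minimum blast level and no stated relation to CR/CRp/CRi, PR or relapse, so one marrow can meet two categories with opposite consequences for treatment

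*Combined protocol and SAP*

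**What the plan says.** **PD (12.2.5).** An "Increase in the absolute number of circulating (in peripheral blood) or bone marrow blasts of at least 50% from nadir", or new extramedullary disease. There is no minimum blast level, no confirming marrow and no exclusion of patients in remission.

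**Remission (12.2.1 to 12.2.3).** On the marrow side, all three categories need only M1, and 12.2.9 states that "M1 is < 5% blasts". CR is "Attainment of an M1 bone marrow (< 5% blasts) with no evidence of circulating blasts or extramedullary disease", plus recovery of ANC and platelets. CRp and CRi use the same marrow and disease conditions with weaker count requirements.

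**PR (12.2.4).** A fall of at least half in the marrow blast percentage, to between 5% and 25%.

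**SD (12.2.6).** Whatever meets none of the other categories. No order of precedence is given.

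**Relapse (12.2.7).** "Morphologic relapse after CR/CRp/CRI is defined as a reappearance of leukemic blasts in the peripheral blood", or at least 5% marrow blasts not otherwise explained. A repeat marrow is required in certain cases.

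**Consequences.** Section 2.5: "If a patient experiences progressive disease at any time point, they must discontinue protocol therapy". Section 5.2 says the same about subsequent cycles. Criterion 10.1(a) lists progressive disease as a reason for removal and refers to Section 12; relapse is not listed separately. Under 2.5 and 5.1, at least a PR following Cycle 2 permits continuation up to six cycles.

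**The concern.** Response categories should be mutually exclusive, or the plan should rank them. Here PD is a relative rule without a lower limit, while remission is defined by an upper limit. Any rise of half that stays below 5% therefore satisfies both on the marrow side. At blast percentages this low, such a rise is often within the counting error of a marrow differential.

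Section 12.2.7 treats the same patients differently, by a 5% marrow criterion with repeat marrows in stated cases. The mandatory stop, however, is attached to PD and not to relapse. Two investigators could classify the same marrow differently, and one reading takes the patient off therapy. Activity is a secondary aim (1.2.2), so the response table would inherit the difference.

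The PD sentence also speaks of an absolute number of blasts, whereas every marrow category in 12.2 is a percentage. The protocol gives no way to obtain an absolute marrow blast count.

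**Working it through.** The plan gives no figure to reproduce here. The check applies the written rules to marrow values and then illustrates counting error.

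**1. Remission and PD.** PD is met if (current − nadir) / nadir ≥ 0.50. M1 is met if current < 5%. Cellularity is taken as unchanged.

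| Nadir | Current | Rise | PD | M1 | 5% relapse criterion |
|---|---|---|---|---|---|
| 2% | 3% | (3 − 2)/2 = 50% | yes | yes | not met |
| 1% | 2% | (2 − 1)/1 = 100% | yes | yes | not met |
| 3% | 4.5% | 1.5/3 = 50% | yes | yes | not met |
| 2% | 2.9% | 0.9/2 = 45% | no | yes | not met |
| 3% | 4% | 1/3 = 33% | no | yes | not met |

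Both rules can be met whenever 1.5 × nadir < 5%, that is, for any non-zero nadir below 5/1.5 = 3.33%. From a nadir of 0% the percentage rise is undefined. The marrow alone does not make a remission: circulating and extramedullary disease must also be absent, and blood counts then decide between CR, CRp and CRi.

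**2. PR and PD.** Baseline 60%, nadir 10%, current 15%. The fall from baseline is (60 − 15)/60 = 75%, and 15% lies within 5% to 25%, so PR is met. The rise from nadir is (15 − 10)/10 = 50%, so PD is met.

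**3. The word absolute.** Read literally, the absolute ratio equals the percentage ratio times the cellularity ratio. For 2% to 3%:
- unchanged cellularity: 1.5 × 1 = 1.5, PD;
- cellularity ratio 1.25: 1.5 × 1.25 = 1.875, PD;
- cellularity ratio 0.8: 1.5 × 0.8 = 1.2, not PD.

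The overlap survives at 0.8 with a larger rise: 2% to 3.75% gives 1.875 × 0.8 = 1.5, and 3.75% is still M1.

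**4. Counting error (illustration).** Assumptions not in the documents: 200 or 500 cells counted, and true blasts constant at 2% or 3%. With X1 and X2 independent Binomial(n, p), the quantity is P(X2 ≥ 1.5·X1 given X1 > 0). The last column also requires X2/n < 5%.

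| True blasts | Cells | Probability | And still under 5% |
|---|---|---|---|
| 2% | 200 | 30.7% | 30.0% |
| 2% | 500 | 20.1% | 20.1% |
| 3% | 200 | 26.6% | 20.9% |
| 3% | 500 | 14.5% | 13.7% |

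These are per pair of marrows. Section 8.1 schedules a marrow at the end of every cycle, and the comparator is the lowest earlier value, so repeated looks would raise the chance of at least one such rise.

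**The case against.** **Section 12.2.7 already covers patients in remission.** It requires a repeat marrow when flow cytometry suggests relapse at under 5% blasts, which would have little purpose if a move from 2% to 3% were already PD. This is the strongest point, and it suggests what the authors probably meant. It does not settle the matter: no text says 12.2.7 replaces 12.2.5, and the stopping rules name PD.

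**Mandatory wording outranks permissive wording.** One can argue that the PD stop prevails over the permission to continue with PR. That would decide treatment on that reading, but not which category enters the response table.

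**Regeneration is recognised.** Section 12.2.1 allows flow cytometry to distinguish regeneration from leukemia, and 12.2.4 allows a repeat marrow. Neither modifies the PD rule. Leaving it to judgment means PD calls may differ by site.

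**Best response is corrupted.** A reader might infer this, but the documents do not support it. Section 12.2 takes best response over up to four cycles, so a remission already reached is normally kept. What a PD call can block is an upgrade, such as CRi to CR.

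**PR depends on the PD call.** This too might be inferred. The PR definition does not mention PD; only SD is defined by exclusion of PD.

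**Few patients are exposed.** Section 2.3.1 reports CR/CRi in 5 of 27 response-evaluable adults (19%). If that rate held among the 27 patients anticipated in 11.1, about 27 × 5/27 = 5 would be at risk of the remission overlap, and fewer if remitters proceed to transplant as 12.2 anticipates. This limits the scale without removing the contradiction.

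**Conclusion.** The contradiction stands on the text. Followed literally, 12.2.5 places some marrows in PD and in CR, CRp or CRi at the same visit, and others in PD and PR, with opposite consequences for continuing therapy. For patients after remission, 12.2.5 and 12.2.7 conflict and nothing ranks them.

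The 2% to 3% example lies exactly on the 50% limit and assumes unchanged cellularity. The overlap itself does not depend on that one example. The probabilities of about 31% and 20% at 2% (27% and 14% at 3%) rest on assumed cell counts and constant true blast levels. They should not be read as the share of responders who would actually be removed.

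The effect is confined to response classification, which 11.5 reports descriptively, and to who leaves therapy. The DLT and MTD rules do not use these categories. The point is worth correcting before response is classified, but it does not threaten the primary aim.

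**What to change.** Reconcile 12.2.1 to 12.2.7 with each other and with 2.5, 5.1, 5.2 and 10.1, so that each marrow result falls in one category. The text should state:
- whether 12.2.5 or 12.2.7 governs patients in CR, CRp or CRi;
- which category prevails when two are met, including PR and PD;
- whether marrow blasts are compared as a percentage or an absolute number, and, if absolute, how that number is obtained.

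Which threshold and which stopping rule apply is for the sponsor to decide; this review proposes neither. The cost is a few sentences and no new data, unless an absolute marrow count is chosen. The downside is small: some PD calls may come at a different time than under a literal reading of 12.2.5.

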12.2.6 Stable Disease (SD)

Criteria for CR, CRp, CRI, CRc, PR, or progressive disease (PD) not met.

12.2.7 Relapse

Morphologic relapse after CR/CRp/CRI is defined as a reappearance of leukemic blasts in the peripheral blood or $\geq 5\%$ blasts in the bone marrow not attributable to any other cause (e.g., bone marrow regeneration after consolidation therapy). In the setting of recent treatment, if there are no circulating blasts and the bone marrow contains 5% to 20% blasts, a repeat bone marrow performed at least a week later is necessary to distinguish relapse from bone marrow regeneration. Should flow cytometric analyses suggest relapse (by the reappearance of a similar immunophenotype to the original leukemia) in the presence of < 5% blasts, or $\geq 5\%$ blasts in a regenerating marrow, a repeat bone marrow(s) performed at least a week later is necessary to confirm relapse by morphologic methods. In such instances the date of recurrence is defined as the first date that more than 5% blasts were observed in the marrow. The

THIS PROTOCOL IS FOR RESEARCH PURPOSES ONLY, SEE PAGE 1 FOR USAGE POLICY

reappearance or development of cytologically proven extramedullary disease also indicates relapse. Molecular and/or genetic relapse is characterized by reappearance of a cytogenetics or molecular abnormality.

12.2.8 Unevaluable

Aplastic or severely hypocellular marrow with any blast percentage. In this instance, marrow evaluation should be repeated weekly until response determination can be made through at least Day 49.

12.2.9 Bone Marrow Classification:

M1 is < 5% blasts
M2 is 5-25% blasts
M3 is > 25% blasts

12.3 CNS Leukemia at Diagnosis

CNS 1:	In cerebral spinal fluid (CSF), absence of blasts on cytopspin preparation, regardless of the number of WBCs.
CNS 2:	In CSF, presence $< 5/\mu\text{L}$ WBCs and cytopspin positive for blasts, or $\geq 5/\mu\text{L}$ WBCs but negative by Steinherz/Bleyer algorithm:
CNS 2a:	$< 10/\mu\text{L}$ RBCs; $< 5/\mu\text{L}$ WBCs and cytopspin positive for blasts;
CNS 2b:	$\geq 10/\mu\text{L}$ RBCs; $< 5/\mu\text{L}$ WBCs and cytopspin positive for blasts;
CNS 2c:	$\geq 10/\mu\text{L}$ RBCs; $\geq 5/\mu\text{L}$ WBCs and cytopspin positive for blasts, but negative by Steinherz/Bleyer algorithm (see below).
CNS 3:	In CSF, presence of $\geq 5/\mu\text{L}$ WBCs and cytopspin positive for blasts and/or clinical signs of CNS leukemia:
CNS 3a:	$< 10/\mu\text{L}$ RBCs; $\geq 5/\mu\text{L}$ WBCs and cytopspin positive for blasts;
CNS 3b:	$\geq 10/\mu\text{L}$ RBCs, $\geq 5/\mu\text{L}$ WBCs and positive by Steinherz/Bleyer algorithm (see below);
CNS 3c:	Clinical signs of CNS leukemia (such as facial nerve palsy, brain/eye involvement or hypothalamic syndrome).

Method of Evaluating Initial Traumatic Lumbar Punctures:

If the patient has leukemic cells in the peripheral blood and the lumbar puncture is traumatic and contains $\geq 5 \text{ WBC}/\mu\text{L}$ and blasts, the following algorithm should be used to distinguish between CNS 2 and CNS 3 disease:

$$\frac{\text{CSF WBC}}{\text{CSF RBC}} > 2 \times \frac{\text{Blood WBC}}{\text{Blood RBC}}$$

A patient with CSF WBC $\geq 5/\mu\text{L}$ blasts, whose CSF WBC/RBC is 2X greater than the blood WBC/RBC ratio, has CNS disease at diagnosis. Example: CSF WBC = $60/\mu\text{L}$; CSF RBC = $1500/\mu\text{L}$; blood WBC = $46000/\mu\text{L}$; blood RBC = $3.0 \times 10^6/\mu\text{L}$:

$$\frac{60}{1,500} = 0.04 > 2 \times \frac{46,000}{3.0 \times 10^6} = 0.015$$

